2.1.3 Visit, baseline and post baseline definitions

Except for biomarkers (described in Section 2.2.7.3), discharge visit will be mapped to Day 1, 2, 3, 4, 5, 14 (with +/- 3 day window), 60 (with +/- 7 days window), 120 (with +/- 7 days window), 180 (with +/- 7 day window) if the scheduled visits are missing.

Screening phase: The screening phase is defined as the period prior to randomization. After obtaining written informed consent, the subject will be evaluated for eligibility to participate in to the study.

Baseline definition for efficacy/safety measurements: Baseline is defined as Hour 0/Day 1 assessment. The baseline date and time will be considered the date and time of initiation of study drug, or randomization if the subject was not treated with study drug. If missing, the value at screening visit will be used.

Post-baseline phase for efficacy/safety measurements: The post-baseline phase begins at the time when study drug administration starts (Hour 0/Day 1) and ends with the last study assessment/last follow-up or the death of subject. For subjects who did not receive study drug, the phase begins at time of randomization.

2.1.4 Subgroup definitions

If not otherwise specified, the following subgroups will be defined for the study using the data collected at screening.

The key subgroups will be used in primary and key secondary endpoints.

Table 2-3 Specification of key subgroups at screening

Subgroup	Method of Derivation
Age groups (<65, ≥65; <75, ≥75 years)	Derived
Gender	eCRF
Race (White/Caucasian, Other)	Derived
Region *	Derived
Ejection fractions (<50%, ≥50%; <40%, ≥40%)	Derived
Prior history of heart failure (yes/no)	eCRF

* **North America:** USA, Canada

Latin America (including Central America): Argentina, Brazil, Chile, Colombia, Peru, Mexico

Western Europe: Austria, Belgium, Denmark, France, Germany, Greece, Ireland, Italy, Netherlands, Norway, Portugal, Spain, Sweden, Switzerland, UK, Turkey, Israel

Of note, Turkey and Israel are classified in Western Europe based on medical practice.

Eastern Europe: Bulgaria, Czech Republic, Hungary, Poland, Slovakia, Romania, Russia

Other: Australia, South Africa

Additional exploratory subgroups analysis (as defined in Table 2-4, based on [Metra et al 2013](#)) of primary and key secondary time to event endpoints will be presented in Appendix 16.1.9 only.

Table 2-4 Specification of additional subgroups at screening

Subgroup	Method of Derivation
NT-proBNP ≥ 3000 pg/ml or BNP ≥ 750 pg/ml	Local lab, Derived
Systolic blood pressure (<140, ≥140 mmHg)	Derived
Heart rate (< 80, ≥ 80 bpm)	Derived
History of Ischemic heart disease (yes/no)	eCRF
History of diabetic mellitus (yes/no)	eCRF
History of atrial fibrillation or flutter (yes/no)	eCRF

Time from presentation to randomization (<2, 2-10, >10 hours)	Derived
Intravenous (IV) nitrate use at randomization (yes/no)	eCRF
eGFR (<30, ≥30; <50, ≥50; <60, ≥60 mL/min/1.73 m ²)	Local Lab, Derived

2.1.5 Subject disposition

The number of subjects randomized and included in the full analysis set (FAS) will be presented by treatment group. The number of subjects screened only (SCR) will be presented. In addition, the reasons for screen failures will be provided. The number and percentage of subjects in the FAS who completed the study, who discontinued the study and the reason for discontinuation will be presented for each treatment group and all subjects.

A completer will be defined as either has died with adjudicated cause (including those adjudicated as having unknown cause), or whose actual follow up is greater or equal to 165 days (last known vital status – baseline date).

The frequency (%) of subjects with protocol deviations as well as the criteria leading to exclusion from analysis sets will be presented for RAN.

The number of subjects enrolled and randomized per region and country will be presented for FAS.

For each subject, the length of follow-up (days) will be computed by subtracting the study drug initiation date (or the randomization date for subjects not treated with study drug) from the end of study date (the last known vital status).

Descriptive statistics will be presented for length of follow-up by treatment group and overall. Categorical summaries will also be presented for the number and percent of subjects within predefined follow-up intervals as: None; >0-5 days; 6-14 days; 15-60 days; 61-120 days; 121-180 days.

2.1.6 Background and demographic characteristics

Subject demographics (age, sex, ethnicity, race, weight (continuous and <115kg, ≥ 115 kg) and height) and baseline characteristics (including alcohol history and smoking history) will be summarized for the FAS.

For baseline comparability analysis, categorical variables will be analyzed using the Chi-square test and continuous variables will be analyzed using the t-test and will be presented in Appendix 16.1.9 only.

The p-values will be provided for descriptive purpose and will not be considered to define any formal basis for determining factors to be included in statistical models. If an imbalance of treatment groups with respect to some variables does occur, supplemental analyses with addition of these variables in model may be performed to assess the potential impact on efficacy as appropriate.

The background and demographic characteristics analysis will be repeated for age, gender, race, region, PEF/REF and history of HF subgroups as defined in Table 2-2 for the FAS. The results will be presented as supplementary analysis in the statistical Appendix section.

Baseline characteristics of interest in vital signs and local laboratory values collected at screening visit will also be presented for the FAS.

2.1.7 Medical history

The number and percentage of subjects including but not limited to who had history of heart failure, New York Heart Association (NYHA) class, primary heart failure etiology (ischemic/non-ischemic), who were hospitalized for heart failure, ejection fraction (<40%, ≥40%; <50%, ≥50%), who were on heart transplant list, and who had history of diabetes mellitus will be presented for FAS. The number of HF hospitalization in the past year and ejection fraction (%) will also be presented.

The number and percentage of subjects will also be presented for each protocol solicited event as pre-printed list in eCRFs for the FAS.

Any other condition entered on the medical history not recorded on the medical history protocol solicited events or heart failure history eCRFs will be coded using the MedDRA dictionary. The number and percentage of subjects with each medical condition will be provided by treatment group for the FAS.

2.1.8 Other subject history information

The number and percentage of subject in lifestyle history, highest level of education and home health care arrangement, will be presented for the FAS.

The history drug abuse will also be presented for the FAS.

2.1.9 Study medication

For the FAS population, study drug administration details will be summarized by treatment group and overall for the time from presentation to hospital (hours), time from first IV loop diuretic for the current AHF episode to randomization (hours), time from earlier of presentation to hospital or first IV loop diuretic to randomization (hours), time from randomization to study drug administration (hours), on IV nitrates at randomization (yes/no), dose decreased due to blood pressure decrease (yes/no), study drug administered on either day (yes/no), reason study drug not administered, actual study drug received, and the number of days infused (one or two days), study drug prematurely discontinued and reasons for discontinuation.

The duration of study drug administration (in hours) and the total volume of study drug administered (estimated from infusion duration at each infusion rate) will also be summarized by treatment group and overall.

2.1.10 Concomitant medication

The use of all concomitant medications will be summarized using the SAF population.

2.1.10.1 IV loop diuretic medications

IV loop diuretic medications include the following:

- Bumetanide

- Etacrynic acid/Ethacrynic acid
- Furosemide
- Torasemide/Torseamide

The number and percentage of subjects using IV loop diuretic medications will be summarized for each of the time periods: Hour 24/Day 1 to end of study, Hour 0/Day 1, 24 hours/Day 1, 48 hours/Day 2, Day 3, Day 4, Day 5, and Discharge. Each time point reflects medication use within the preceding 24 hours.

The average total daily dose for each medication will also be presented at reported time point. In addition, cumulative use reported at 48 Hours (24 hours/Day 1 and 48 hours/Day 2), and at Day 5 (from 24 hours/Day 1 to Day 5) in furosemide equivalent (mg) will be summarized. The calculation of furosemide equivalents (mg) for Bumetanide, Ethacrynic acid/Ethacrynic acid and Torsemide/Torseamide acid are actual dose (mg) multiplied by constant 40, 0.8, or 2, respectively. For subjects who die before Day 5, the minimum of 2 times of the last recorded dose and 160 mg will be assumed for every day from the date of death up to and including Day 5.

2.1.10.2 IV medications other than loop diuretics

The number of subjects using other IV medications including Dopamine, Dobutamine, Milirinone, Enoximone, Norepinephrine, Epinephrine, Nesiritide, Levosimendan, Isosorbide Dinitrate, Nitroglycerin, Nitroprusside, Phenylephrine and other will be presented in the same way as IV loop diuretic medications.

The average dose over the time administered of the medication will be presented separately for each medication at each reported time point. No equivalent dose unit among other IV medications will be converted.

2.1.10.3 Other non-IV concomitant medications

The use of other non-IV concomitant medications is reported through Day 180. The number and percentage of subjects using other non-IV medications will be summarized for each of the time periods: 30 days to 14 prior to study drug initiation, Hour 24/Day 1 to end of study, Hour 0/Day 1, 24 hours/Day 1, 48 hours/Day 2, Day 3, Day 4, Day 5, Discharge, Day 14, Day 60, Day 120 and Day 180 for ACE inhibitor (ACEi), angiotensin inhibitor (ARB), ACEi or ARB, beta blocker, PO loop diuretics, other PO diuretics, calcium channel blockers, aldosterone antagonist and cardiac glycosides.

In addition, the number (%) of subjects who have these medications initiated during their index hospitalization and subjects who have these medications increased during the period following discharge from the index hospitalization will also be presented.

The average daily dose administered will be summarized at each time point for each medication within the loop diuretics, ACEi, ARB, beta blocker, aldosterone antagonist, ARNi and direct renin inhibitor. .

Other non-IV concomitant medications taken prior to, and after the start of study drug will be presented by the ATC and preferred terms.

2.1.11 Close-out procedure

The number of CV deaths will be predicted on an ongoing basis. [REDACTED]

Subjects who have been randomized to the study will be followed up until their final visit (180 days) or date of death. Attempts should be made to contact any subjects who did not complete the Day 180 visit.

The aim of the close-out procedure will be to allow for all necessary activities (study completion visits, data cleaning, raising and resolution of all queries to the clinical sites, etc.) including the adjudication of all primary and secondary events that occurred during the study and prior to final visit. The “adjudicated endpoint” refers to an endpoint and date of the endpoint that has been confirmed by an independent endpoint committee who has no access to the treatment code.

Only adjudicated events will be counted in the primary analyses. However, sensitivity analyses will be performed on the suspected (investigator reported) primary and secondary endpoints.

2.2 Efficacy evaluation

The primary analysis and the analyses of all secondary efficacy endpoints will be based on the FAS population following the intention-to-treat principle.

[figure not shown]
2.2.1 Efficacy variables

The following table gives an overview of efficacy variables.

Table 2-5 Primary, secondary and exploratory variables

Variables	Analysis set	Analysis method
Primary efficacy variables		
1 Time to CV death through Day 180	FAS/PPS	log rank test and Kaplan-Meier estimates
2 Time to worsening heart failure (WHF) through Day 5 (considering death in the 5-day period as WHF event)	FAS/PPS	Gehan’s generalized Wilcoxon test
Secondary efficacy variables (if either primary variable is significant, follow sequential testing procedure)		
1 Time to all-cause death through Day 180	FAS/PPS	log rank test and Kaplan-Meier estimates (of note: will not be formally incorporated in a multiple testing procedure)
2 Length of total hospital stay (LOS) during the index AHF hospitalization	FAS/PPS	Wilcoxon rank-sum test
3 Time to first occurrence of the composite endpoint of CV death or rehospitalization due to heart failure (HF)/renal failure (RF) through Day 180	FAS/PPS	log rank test and Kaplan-Meier estimates
Other secondary efficacy endpoints (at $\alpha=0.05$, no multiplicity adjustment)		

Variables	Analysis set	Analysis method
1 Length of ICU and/or CCU stay for the index AHF hospitalization	FAS	Wilcoxon rank-sum test
2 Change from baseline in congestive signs and symptoms of HF through Day 5	FAS	Wilcoxon rank-sum test at each post-baseline visit
3 Change from baseline in selected biomarkers from baseline through Day 14 in a subset of randomized subjects	FAS	Repeated measurement model

Primary and key secondary endpoints are considered in sequential testing procedure and efficacy interim analysis

For the time to **confirmed** CV death during the follow-up period of 180 days, the confirmation of primary events is based on an adjudication process through an independent CEC (Clinical Endpoint Committee). The CEC will also adjudicate all recurrent events of the unplanned hospitalizations according to the protocol.

2.2.2 Definition of time to CV death through Day 180

Events that occur prior to or at the subject's final visit date will be part of the time-to-event analyses. Events that occurred more than 180 days will be considered as censored from the analyses. The CV death will be based on adjudicated results. If the adjudicated cause of death is unknown, it will be considered as a CV death.

The time-to-event for a given subject will be calculated as the difference between the subject's date of endpoint and the randomization date:

- Time-to-event (days) = date of CV death – randomization date,

For those subjects without events, the censoring date will be the earliest in the following dates:

- **180 days**
- **Date subject withdrew consent to all follow-up (if no subsequent vital status documented)**

Note: in accordance with local laws and regulations, vital status may be publically available

- **Date of non-CV death**
- **Date of subject's last visit or contact or vital status**

The censoring time for the analyses will be calculated as:

- Time-to-event censored (days) = censoring date – randomization date

Whenever the event date or visit date needed for defining the time-to-event or censoring date is missing or incomplete for a given subject, an imputation rule for missing/incomplete date will be applied. More details about the imputation rule are presented in [Section 2.2.9](#).

2.2.3 Time to worsening heart failure (WHF) through Day 5 (considering death in the 5-day period as WHF event)

WHF events occurring within 120 hours of randomization will be included in the analysis. WHF is defined as clinical worsening of HF during the index hospitalization or as adjudicated rehospitalization for HF. A subject who dies by 120 hours without a WHF event will be considered to have had an event at the time of death.

Event date and time will be used at calculating the time to event for better precision, and convert it back to days.

Time-to-event (days) = (first event date/time – randomization date/time),

For those subjects without events the censoring date will be the earliest in the following dates:

- **Hour 120 (5 days)**
- **Date subject withdrew consent to all follow-up**
- **Date of subject's last visit or contact**

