Time points	Hour -16	Hour 0 (Day 1)	Hour 6 (Day 1)	Hour 12 (Day 1)	Hour 24 (Day 1)	Hour 48 (Day 2)	Hour 72 (Day 3)	Hour 96 (Day 4)	Hour 120 (Day 5) b	Discharge e	Day 14	Day 60	Day 120	Day 180 /PSW
Visits	1	101	102	103	104	105	106	107	108		109	110	111	199
Assessment of readmission											X	X	X	X
Administer study medication		X												
Contact IRT/IWRS		X			X									
Adverse and serious adverse events m		X			X	X	X	X	X	X	X			
Follow up completion form														X
Withdrawal of Informed Consent Form p	X													X

PSW = premature patient withdrawal; X= assessment to be recorded on clinical database; S= assessment to be recorded on source documentation

a Study drug treatment will be administered as continuous intravenous infusion for up to 48 hours. Dosage can be adjusted under specific circumstances as described in [Section 5.5.5](#)

b Patients discharged prior to Day 5 will return to the hospital/clinic for Day 5 procedures. Patients unable or unwilling to return to the hospital/clinic will be contacted on or after Day 5 by telephone to obtain information about AEs/SAEs, potential endpoints and survival status.

c Patients discharged prior to Day 14 will return to the hospital/clinic for Day 14 procedures. Patients unable or unwilling to return to the hospital/clinic will be contacted on or after Day 14 by telephone to obtain information about SAEs, potential endpoints and survival status. The Day 60 and Day 180 assessments will be conducted as outpatient visits if the patient is discharged prior. The Day 180 assessments can be performed as early as - 7 days from the timepoint. The Day 120 assessment will be conducted by telephone. Patients unable or unwilling to return to the hospital/clinic for scheduled outpatient visits will be contacted by telephone as close as possible to the expected visit to obtain information about endpoints and survival status. If a patient fails to return for the remaining outpatient visit(s) the investigator should show “due diligence” by contacting the patient, family or family physician up to the time of database lock.

d Procedures performed as part of a site’s standard of care for an individual with AHF can be done during the pre-screening interval and may pre-date the signed ICF.

e If Discharge Visit coincides with a scheduled visit, only the Discharge Visit will be performed.

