r The echocardiogram should be performed as soon as possible post randomization, but prior to discharge. If an echocardiogram is performed during the screening period (i.e. within the 16 hours window) and the patient is subsequently randomized, the screening echocardiogram will qualify as the index hospitalization echocardiogram and a repeat echocardiogram post randomization will not be necessary.

s At hours 24, 48, 72, 96 and 120, physician assessment of HF signs and symptoms will include an assessment of the occurrence of worsening heart failure in the interval preceding the visit. These evaluations should be done at approximately the same time of day, each day, in the same position, and hospital/clinic setting, preferably by the same assessor. Refer to [Section 6.4.4](#).

t Body weight measurements performed during hospitalization can be performed anytime

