## 6.4 Efficacy

### 6.4.1 Efficacy assessment 1

- The primary efficacy endpoint is defined as the time to confirmed CV death during a follow-up period of 180 days.
- Time to first occurrence of worsening heart failure\* through Day 5 (considering death in the 5-day period as WHF event)

*\* Worsening heart failure through Day 5 post randomization, includes worsening signs and/or symptoms of heart failure that require an intensification of intravenous therapy for heart failure or mechanical ventilatory, renal or circulatory support. Such treatment can include the institution or up-titration of IV diuretic, IV nitrates or any other IV medication for heart failure, or institution of mechanical support such as mechanical ventilation, ultrafiltration, hemodialysis, intra-aortic balloon pump or ventricular assist device, etc. WHF can occur either during the index admission, or after discharge as an unplanned rehospitalization or unscheduled physician office/emergency department visit due to a primary diagnosis of HF.*

*This endpoint also includes patients who die in this 5-day period of any cause before experiencing episode(s) of WHF.*

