##### **6.4.4.2 Rehospitalization**

Rehospitalization will be defined as all unplanned hospitalization (including admission to a hospital or any attendance in an acute care setting e.g. ED, or in another health care facility) of 24 hours or greater, regardless of whether the patient was admitted to the hospital.

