### **6.6.2 Resource utilization**

Analyses will be undertaken, as appropriate, to assess the effects of treatments on healthcare resource utilization (RU) parameters.

At Visit 1 (screening), prior heart failure hospitalizations, relevant medical conditions and therapies, and prior procedures will be collected. Throughout the index hospitalization, the level of health care resource utilization will be assessed by the overall length of stay, length of time in specific inpatient care units, and procedures rendered during hospital stay. The frequency and duration of subsequent inpatient hospitalization will be recorded along with the primary reason for the hospital admission and discharge, length of time in specific inpatient care units, and procedures rendered. The frequency of urgent care for AHF lasting more than 24 hours and the procedures rendered will also be recorded.

All attempts will be made to collect RU variables in all patients throughout the duration of the study in order to avoid selection bias. There may also be circumstances when the collection of such data after completion of the study may be warranted.

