The CRLX030A2301 study (also referred to as RELAX-AHF-2) aims to evaluate the efficacy, safety and tolerability of intravenous infusion of 30 µg/kg/day serelaxin for 48 hours, when added to standard therapy. Data from this study is intended to replicate the reduction in mortality in AHF patients observed in the RELAX-AHF study.

The purpose of this document is to outline the planned analyses to be completed to support the completion of the Clinical Study Report (CSR) for RELAX AHF-2.

2 Statistical methods planned in the protocol and determination of sample size

Data will be analyzed according to the data analysis section 10 of the study protocol which is available in [Appendix 16.1.1 of the CSR](#).

All nominal time points will be used for analysis; actual assessment times will not be used to reclassify the time point at which a measure was taken. Time-to-event analyses will be based on actual dates (time) reported.

All references to index hospitalization refer to the initial hospitalization for AHF.

Unless specified, descriptive statistics indicates mean, median, standard deviation, minimum and maximum will be presented for continuous variables; the number and percentage of subjects in each category will be presented for categorical variables for each treatment group and all subjects (total).

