2.2.7.1 Length of ICU and/or CCU stay for the index AHF hospitalization

The days stayed in ICU/CCU will be obtained from eCRF page directly. If subjects die during the initial hospitalization, the maximum number of days plus 1 day in the ICU/CCU over all subjects will be assigned.

The length of ICU and/or CCU stay for the index AHF hospitalization will be analyzed similarly to the length of hospital stay, i.e., it will be compared using a Wilcoxon rank sum

test. As a sensitivity analysis, the van Elteren extension to the Wilcoxon rank sum test will also be carried out stratifying for region.

2.2.7.2 Change from baseline in congestive signs and symptoms of HF through Day 5

Detailed criteria to assess subject's signs and symptoms (dyspnea on exertion, orthopnea, edema, rales, and jugular venous pulse) of heart failure can be found in protocol Appendix 15.

Subjects who die or have a worsening heart failure event (either during the index hospital or rehospitalization due to heart failure) will have their score imputed to be the worst observed score in any subject at any time point in the respective analysis population carried forward from the day of death or WHF regardless of whether their original data are missing through Day 5. For patients who are alive with missing values, the last preceding non-missing value will be used for imputation.

A time-to-event (response defined as ≥ 1 point improvement from baseline) analysis will be applied to provide treatment comparisons. Hazard ratios (serelaxin/placebo) of being a responder for each of the signs and symptoms variables will be estimated using a Cox regression model stratified by region with treatment as a factor.

Since the assessment only occurs on the scheduled visits, the nominal scheduled day will be used directly to determine the time to event with exact handling of ties.

For those subjects without events, the censoring date will be the earliest in the following dates:

- **6 days**
- **Date subject withdrew consent to all follow-up**
- **Date of subject's last visit or contact**

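### The SAP's definition of the WHF primary endpoint omits the post-discharge office and short emergency-visit route that the protocol counts, and does not repeat the protocol's treatment requirement

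*SAP*

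**What the plan says.** **Protocol.** Section 6.4.1, repeated in the synopsis, defines WHF through Day 5 as worsening signs and/or symptoms that need intensified intravenous therapy or mechanical support. It may occur in the index admission or "after discharge as an unplanned rehospitalization or unscheduled physician office/emergency department visit due to a primary diagnosis of HF". Death from any cause within the five days also counts. Section 6.4.4.2 lets rehospitalization include emergency department attendance, but only "of 24 hours or greater, regardless of whether the patient was admitted to the hospital".

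**SAP.** Section 2.2.3 says that "WHF is defined as clinical worsening of HF during the index hospitalization or as adjudicated rehospitalization for HF"; a patient who dies by 120 hours without WHF is counted at the time of death. Section 2.2.7.2 names the same two settings when it imputes scores for patients who "have a worsening heart failure event (either during the index hospital or rehospitalization due to heart failure". The opening of SAP section 2 says "Data will be analyzed according to the data analysis section 10 of the study protocol", but protocol section 10 does not list the qualifying settings. The SAP document history records no change to the WHF definition.

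**Data capture.** At hours 24 to 120 the physician assessment "will include an assessment of the occurrence of worsening heart failure in the interval preceding the visit" (protocol Table 6-1, footnote s). Patients who cannot or will not return for Day 5 "will be contacted on or after Day 5 by telephone to obtain information about AEs/SAEs, potential endpoints and survival status" (footnote b). The resource-use section (6.6.2) says "The frequency of urgent care for AHF lasting more than 24 hours and the procedures rendered will also be recorded".

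**The concern.** WHF is one of two primary endpoints. It has its own initial one-sided level of 0.005, and its success alone opens the tests of all-cause death and the other key secondary variables. If the two governing documents disagree on which patients have the event, the endpoint tested may not be the endpoint defined. A program written from SAP 2.2.3 would code as event-free a patient who went home, returned on Day 4 to an emergency department for a few hours of intensified intravenous treatment, and had no other WHF event or death in the window. Protocol 6.4.1 counts that patient. If the discrepancy is noticed only after unblinding, either choice of definition is open to challenge.

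**Working it through.** **1. The two definitions applied to the same patient, events within 120 hours of randomization**

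| Situation | Protocol 6.4.1 | SAP 2.2.3 as written |
|---|---|---|
| Worsening in the index admission, treatment intensified | event | event |
| Clinical worsening in the index admission, treatment not intensified | no event | event, if read literally |
| After discharge, HF stay of 24 h or more, treatment intensified | event | event, if adjudicated as HF |
| After discharge, HF emergency visit under 24 h, treatment intensified | event | no event |
| After discharge, HF office visit under 24 h, treatment intensified | event | no event |
| After discharge, HF visit under 24 h, treatment not intensified | no event | no event |
| Death without earlier WHF | event | event |

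The 120-hour window, the death rule and the randomization time origin agree. The definitions differ in rows 2, 4 and 5. A patient in row 4 or 5 changes status only if no other WHF event or death falls in the window. If a qualifying rehospitalization or death follows, the patient still counts, with a later event time.

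**2. The plan's own WHF power**

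Inputs: 6,800 patients randomized 1:1, so 3,400 per arm; placebo WHF rate 12.2%; HR 0.80 or 0.70; initial WHF level 0.005 one-sided; WHF level after CV death is rejected 0.6 × 0.025 = 0.015 (SAP 2.4). The plan states 81–82% power at HR 0.80 and 99% at HR 0.70, using a logrank approximation.

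- Events at HR 0.80: 3,400 × [0.122 + (1 − 0.878^0.8)] = 414.8 + 336.1 = 751. At HR 0.70: 711.
- Power = Φ(½√d · ln(1/HR) − z), where d is the number of events. At HR 0.80: 68.5% at 0.005, 81.3% at 0.015 and 86.4% at 0.025.
- CV death: 329/0.6 ≈ 548 events, HR 0.78, one-sided 0.0192, gives 79.9%.
- Weighting by CV death success, with the two tests treated as independent: 0.799 × 81.3 + 0.201 × 68.5 = 78.7% if WHF stays at 0.015, and 0.799 × 86.4 + 0.201 × 68.5 = 82.8% if it always rises to 0.025.

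A bracket is needed because the transition weights are in a figure that the public text does not show. The stated 81–82% lies inside it. At HR 0.70 the result is at least 99.3%, against 99% stated.

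**3. Illustration of a loss**

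The share lost is assumed, and the lost events are taken to have the same HR as the rest. HR 0.80:

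| Share of WHF events omitted | Events | Power at 0.015 | Power at 0.005 |
|---|---|---|---|
| 0% | 751 | 81.3% | 68.5% |
| 1% | 743 | 80.8% | 67.9% |
| 2% | 736 | 80.4% | 67.4% |
| 5% | 713 | 79.1% | 65.7% |

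At 0.015 this is about 0.4 points per 1% omitted: (81.3 − 79.1)/5 = 0.44. At HR 0.70 a 5% loss moves power at 0.015 from 99.5% to 99.3%. These are fixed-level figures, not the power of the graphical procedure.

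**The case against.** The best defence is that SAP 2.2.3 is a compressed paraphrase. The document history announces no change to WHF, and the abbreviation list includes a term for clinical worsening heart failure that the public text never uses. SAP 2.2.8 is not in the public text, and protocol 9.5 places detailed endpoint definitions in a separate manual. The authors may therefore have meant the protocol definition throughout. That is plausible, and it is why the missing intensification requirement is not called an error here. It does not settle the settings: the sentence is worded as a definition, SAP 2.2.7.2 repeats the same two settings, and nothing in the available text restores the visit route.

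Four stronger readings are tempting, and the documents do not support them.

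- *The SAP is simply narrower, so events and power are lost.* Read literally it is narrower on settings and looser on treatment, so events could be gained as well. SAP 2.2.5 even lists intravenous or mechanical intervention as an example of a modified definition.
- *Losing a given number of events takes power below the promised 80%.* The synopsis figure is for the full multiple testing procedure. The bracket above already straddles 80% with no loss, so a threshold computed at a fixed level has no meaning. The documents also do not say which WHF definition produced the 12.2% rate in the earlier trial. If it was the narrower one, nothing is lost against plan.
- *The 48-hour treatment period caps the time at risk for such visits.* The intravenous therapy is only anticipated at entry, and the infusion may stop early, so this gives no firm bound.
- *SAP 2.1.11 removes in-hospital WHF, because primary analyses count only adjudicated events and protocol 9.5 covers deaths and rehospitalizations.* SAP 2.2.3 attaches adjudication to rehospitalization only and lists in-hospital worsening separately. The specific definition should govern; a clarifying sentence is enough.

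The objection that few patients are affected stands. They must be discharged before 120 hours, need intensified treatment at a visit under 24 hours, and have no other WHF event or death in the window.

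**Conclusion.** The point holds as a mismatch between the documents on which events qualify for a primary endpoint. Under SAP 2.2.3 as written, an office or emergency visit under 24 hours that meets the protocol definition does not count. The treatment requirement is not carried over either, which may be shorthand.

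The number of patients affected is not given and is probably small, and the net direction is unknown. The 0.4 points of power per 1% of events omitted is an illustration only. It rests on assumed loss fractions, a common HR of 0.80 and a fixed one-sided level of 0.015, and it ignores any events gained through the looser treatment wording. A reader might infer bias between arms or type I error inflation; neither is shown, since one definition would apply to both blinded arms. The correction is worth making because the endpoint is primary and the change is easy before unblinding, not because a large effect is expected.

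**What to change.** Before database lock and unblinding:

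1. Make SAP 2.2.3 cite or restate the protocol 6.4.1 definition in full, covering both the care settings and the intensification requirement. Align SAP 2.2.5 and 2.2.7.2 with it.
2. If the narrower SAP definition is intended, state it as a change and run the protocol definition as a sensitivity analysis.
3. Add one sentence to SAP 2.1.11 saying that the adjudicated-only rule applies to deaths and rehospitalizations and not to in-hospital WHF, consistent with SAP 2.2.3 and protocol 9.5.
4. Check that the CRF records office and emergency visits under 24 hours with date and time. Endpoint questions are asked through Day 5, but the one explicit statement on recording urgent care (protocol 6.6.2) is limited to care lasting more than 24 hours. That statement concerns resource use, so it does not show that endpoint data are missing.

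The cost is a few lines of SAP text and one CRF check. The CRF is not among the documents, so whether the visits can be recovered from the database cannot be judged here.
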